Relevance: The studies proposed here will rigorously test the efficacy of FES-based restorative therapies in promoting neurological and functional recovery in patients with SCI. These findings will be applied in a clinical setting to optimize the FES-based therapies.

VII. STUDY DESIGN**a. Background**

Overview: Spinal Cord Injury and related paralysis impose a major socioeconomic burden on those afflicted with this devastating neurologic deficit. At the society level, the estimated annual aggregate cost is over 7 billion 1992 US dollars [5]. There is no cure, but bench research data point to neuro-restorative potential of different interventions. Several different reports support the hypothesis that plasticity occurs at the spinal cord level [6-8], and that maintenance of neural activity in injured areas influences the nervous system modeling and repair through different mechanisms: 1) new synapse formation and strengthening of existing ones, 2) re-myelination, 3) new cell birth. Neuronal activity is necessary for the full development and maintenance of inhibitory circuitry [9-21]. Chemical inhibition of neural activity in culture and in animals, results in reduced numbers of inhibitory synapse connections and can result in nervous system over-activity (such as spasticity) once the blockade is partially removed. New synapse formation and stabilization of excitatory synapses may also require coincident neural input to refine connection selectivity and to maintain connections. Re-myelination of axons that have

been de-myelinated secondary to injury is dependent on optimal electrical activity [22]. The strongest evidence is in the peripheral nervous system but strong data also exist in the central nervous system [23-25]. Stem cells exist in the ventricle lining of the brain and spinal cord of adults. These stem cells are capable of birthing new neurons, oligodendrocytes and astrocytes [26, 27]. Patterned neural activity created by enhancing walking activity in rodents can lead to overall greater production and survival of newly born cells [27]. The survival of injured or newly developed neurons and glia has been shown to be partly dependent upon optimal levels of neural activity [28].

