Military Significance: Traumatic injury to the Central Nervous System (CNS) is an increasing problem for the U.S. military, given the increasing number of soldiers with SCI returning from combat zones. Our proposed project will address this specific need by developing rehabilitative programs and training tools as well as advanced technologies for restoring nerve cell function. Understanding the underlying mechanisms that promote regeneration and recovery, as outlined in this proposal, will contribute to the knowledge base in the field as well as advance current concepts of regeneration. Overall, the aims of this proposal have direct and indirect relevance to military and related civilian populations.

Public Purpose: SCI is a devastating condition that imposes major costs on individuals and society. Close to 12,000 traumatic injuries occur each year in the United States, and approximately 1 million people live with SCI. Moreover, military personnel have returned from combat zones with SCI in the past years. Estimates for lifetime financial burden per individual range from \$500,000 to \$2 million, and costs for SCI patient care in the United States exceed \$7 billion dollars. Including non-traumatic spinal-cord lesions, such as those associated with multiple sclerosis, would quadruple the number and annual cost of U.S. SCI cases [43]. However, virtually all current treatments must be applied shortly after the onset of SCI, as there are not yet effective treatments for the chronic phase of injury [4]. Effective treatment and therapeutic strategies geared toward the chronic injury phase would both improve the lifestyles of people with SCI and decrease their financial burden.

b. Study Design, Research Objectives

Study Design: A 12 months randomized, controlled, single-blinded, in-subject controlled (A-B type) trial will be performed in patients with SCI receiving upper extremity ergometry in combination with FES versus an upper extremities non-FES assisted exercise protocol. Neurological and functional outcome measures will be used at 0, 4, 5, 9, and 12 months to test the efficacy of each intervention.

Specific Aim: Does FES of the upper extremities promote neurological and functional recovery?

Hypothesis 1: Patterned FES of arm and shoulder muscles, via upper extremity ergometry, will improve physical and neurological function in individuals with paralysis resulting from spinal cord injury.

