- 1] allows the stimulation of our proposed list of upper extremity muscles (supraspinatus; infraspinatus; teres major and minor; anterior, middle, or posterior deltoid; biceps; and triceps), which is more than the standard set of muscles (bilateral biceps, triceps and supraspinatus).
- 2] allows to change the timing of the stimulation (On/Off) to produce a smooth cycling motion.

4. FDA approved use description:

The device FDA indication for use are:

1. Relaxation of muscle spasms
2. Prevention or retardation of disuse atrophy
3. Increasing local blood circulation
4. Maintaining or increasing range of motion

5. IDE Info:

Not applicable

c. Study Statistics

1. Primary outcome variable.

Independent Variables

FES or no FES

Dependent Variables: to be measured at 0, 4, 5, 9 and 12months

Severity of gleno-humeral subluxation, measured by X-ray (not measured at 5 months).

Spasticity of the pectoralis, biceps, triceps, and long finger flexor muscles, measured with the Modified Ashworth.

Functional movement of the shoulder, measured with the Capabilities of the Upper Extremity (CUE) test.

Hand function, measured with the Jebsen-Taylor Hand Function (JTHF) and Box and Blocks (BB) tests.

Upper limb function measured with the Action Research Arm test (ARA) test.

Range Of Motion of the upper extremity joints (of the shoulder, elbow, wrist, and fingers/thumbs), measured with goniometry.

Pain, measured with the Numerical Rating Scale (NRS).

Neurological function, measured with the American Spinal Injury Association (ASIA) exam.

2. Secondary outcome variables.

Not applicable

3. Statistical plan including sample size justification and interim data analysis.

Data Analysis: Data will be collected in accordance with each instrument's standardized instructions, with the evaluator being blinded to group assignment. To obtain consistency and facilitate interpretation of the data, we will use means and standard deviations (SDs) to describe normally as well as non-normally distributed variables. Appropriate post-hoc statistical analysis will be used to compare between group means and repeated measures. Baseline tests of homogeneity will be used *a priori*. If statistically significant differences are found after the subjects are randomized to the two groups, they will be corrected in the post-hoc analysis. Results will be considered significant at $P<0.05$.

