Power analysis: Because upper extremity, FES-assisted ergometry training is a new intervention, we based our power analysis on previously completed studies that looked at the effect of FES on muscle mass (50, 51) and cardio-vascular conditioning (52-56). A sample size of 24 will allow us to detect a mean difference between the pre- and post-measures. Some of our outcome measures (CUE, JTHF, BB tests) have been shown to respond to many types of rehabilitative interventions, and we believe they will be particularly responsive to the type of training used here. One of our goals is to use the data obtained in this study to determine the magnitude of the effect so we can design future trials. If the magnitude is very small, however, it is unlikely to be clinically relevant. We would then be more likely to propose intensifying the intervention (e.g., by lengthening the periods of cycling) than to suggest increasing sample size.

4. Early stopping rules.

* Subject medical status:

- Requires significant hospitalization (that would interfere with physiologic processes proposed to be studied through the protocol, i.e. e-stim) – at the discretion of PI.
- Increased pain (more than 3 points increase on the NRS).
- Increased shoulder subluxation (more than 1 cm).
- Decreased range of motion (more than 15 deg).

* Subject not compliant:

- Fails to follow directions.
- Become pregnant.

XII. LABELING & STORAGE OF DATA & SPECIMENS

All paper study documents are stored in locked cabinets at the Broadwaycampus of the KKI-ICSCI. Access to the locked cabinets is strictly limited to the study team members listed on this protocol. The documents with identifiers (such as the consent forms, phone screening forms, and the document that links the subject study # to the identity of the subject) are stored in a study binder in a separate locked cabinet from hard copy data collection forms.

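### Nine instruments are all primary at an unadjusted P<0.05, with no lead outcome, time point, success rule or multiplicity control, so the false-positive risk of the efficacy claim is uncontrolled

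*Combined protocol and SAP*

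**What the plan says.** Section XI.c.1 (Primary outcome variable) gives the presence or absence of FES as the independent variable, followed by "Dependent Variables: to be measured at 0, 4, 5, 9 and 12months". Nine instruments come under that line: X-ray subluxation (not taken at month 5), Modified Ashworth, CUE, Jebsen-Taylor, Box and Blocks, Action Research Arm, range of motion, pain NRS and ASIA. Section XI.c.2 marks secondary outcomes as not applicable.

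Section XI.c.3 describes the analysis in one sentence: "Appropriate post-hoc statistical analysis will be used to compare between group means and repeated measures". The threshold is "Results will be considered significant at" P<0.05. Sidedness is not given. The power paragraph in the same section says "A sample size of 24 will allow us to detect a mean difference between the pre- and post-measures" and states no effect size, SD or power.

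On purpose, the abstract (VI.b, Relevance) says "The studies proposed here will rigorously test the efficacy of FES-based restorative therapies". Section VII.b says "outcome measures will be used at 0, 4, 5, 9, and 12 months to test the efficacy of each intervention", and its Hypothesis 1 is that FES ergometry "will improve physical and neurological function in individuals with paralysis resulting from spinal cord injury". The power paragraph adds a further goal, "to determine the magnitude of the effect so we can design future trials".

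**The concern.** A trial that claims to test efficacy should say beforehand which result would count as FES working. Here nine instruments have equal standing, each is open to its own test at 0.05, and the analysis is called post-hoc. Several instruments can also be scored in more than one way. Ashworth covers four muscle groups, range of motion covers several joints, X-rays are bilateral, and ASIA has motor and sensory parts. There are four post-baseline visits (three for X-ray) and two treatment periods.

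The score, visit, contrast and number of positive instruments needed could therefore all be settled after the data are seen. A significant finding on one of nine could be reported as efficacy, with no stated error rate for that claim.

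**Working it through.** **1. What is fixed and what is open.**

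| Element | Status in the plan |
|---|---|
| Factor compared | Fixed: FES versus no FES (XI.c.1); XI.a.5 also says the FES effect is to be isolated |
| Threshold | Fixed: P<0.05, unadjusted (XI.c.3) |
| Lead outcome | Open: nine primaries, no secondaries |
| Score per instrument | Not defined for the analysis |
| Time point, period handling, model | Open: group means and repeated measures are both mentioned, and the sample-size sentence speaks of pre and post measures |
| Success rule, multiplicity control | None |

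**2. The plan's own figures.** No overall error rate is stated, so there is none to reproduce. The sample size of 24 cannot be reproduced either, because no effect size, SD, power or test is given.

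**3. Illustration A: any one of nine counts.** These assumptions are mine: one two-sided 0.05 test per instrument, so 0.025 in favour of FES, and a common correlation ρ between the test statistics.

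- At ρ = 0, favouring FES: 1 − 0.975^9 = 0.204. Either direction: 1 − 0.95^9 = 0.370.
- At ρ > 0, favouring FES: 1 − ∫ φ(u) · Φ((1.96 − √ρ·u)/√(1−ρ))^9 du, by numerical integration.

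**4. Illustration B: ASIA plus at least one of the other eight.** Hypothesis 1 speaks of physical and neurological function, so a reader might require both. At ρ = 0 this is 0.025 × (1 − 0.975^8) = 0.0046. At ρ > 0 it is the matching integral.

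| ρ | A, favouring FES | A, either direction | B, favouring FES |
|---|---|---|---|
| 0 | 20.4% | 37.0% | 0.5% |
| 0.3 | 16.5% | 32.6% | 1.1% |
| 0.5 | 13.5% | 26.9% | 1.5% |
| 0.7 | 10.1% | 20.2% | 1.9% |
| 0.9 | 6.2% | 12.4% | 2.3% |
| Single test | 2.5% | 5% | – |

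Simulated t tests with 10 or 12 per group agree: 20.2% to 20.5% at ρ = 0 and about 6.4% at ρ = 0.9, favouring FES. CUE, Jebsen-Taylor, Box and Blocks and Action Research Arm all measure arm or hand function, so positive correlation is more plausible than zero. On the other side, more than one test per instrument would raise the figures under A.

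**5. What the remedies can detect.** Completers: 24 − 4 = 20 (IX.b). Power of 80% is assumed.

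- Paired FES minus non-FES difference d, in SDs of the paired differences: noncentral t with noncentrality d·√20 and 17 to 19 df. At 0.05, d ≈ 0.66. At the first Holm step over nine, 0.05/9 = 0.0056, d ≈ 0.90 to 0.91. Power for d = 0.66 at that step is about 45%.
- Month-4 comparison between groups: noncentrality d·√(n/2) and 2n − 2 df. With 12 per group, d ≈ 1.20; with 10 per group, d ≈ 1.32, in SDs of the month 0 to 4 change.

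**6. Carryover.** Let f5 and f9 be the shares of the FES gain still present at months 5 and 9 in the FES-first group. End-of-period values show (1 − f9/2) of the true effect. Changes from period baseline show (1 − f9/2 + f5/2). With f5 = f9 = 0.5, end-of-period values show 75%. With f5 = 0.5 and f9 = 0, changes show 125%. A baseline-adjusted contrast lies between its two unadjusted counterparts.

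**The case against.** The strongest reply is that this is an early study. The power paragraph calls the intervention new, wants the effect size for later trials, and says a very small effect would more likely lead to a more intensive intervention than to a larger sample. With 24 subjects, an exploratory reading is reasonable. It does not settle the matter, because effect estimation is given as one goal among others and the efficacy wording in VI.b and VII.b stands beside a P<0.05 rule. If exploration is the intent, relabelling would be enough.

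Four stronger readings are tempting and should not be drawn:

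- **That the plan has a 20% false-positive rate.** No section says one significant instrument means success. The figure belongs to an assumed rule at zero correlation. Illustration B falls below 2.5%, and it too is constructed, since no section says ASIA is the only neurological instrument.
- **That no contrast is named.** The factor is named, and XI.a.5 says its effect will be isolated. Time point, period handling and model are missing. The pre and post wording concerns sample size and need not describe the analysis.
- **That Ashworth or ASIA would need a new rater to serve as primary.** Table 1 already lists Co-Investigator 1 beside the PI for both.
- **That subluxation is ruled out by its missing month-5 value.** Month 5 matters only if the contrast is adjusted for period baselines.

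A sole primary also has a scientific cost: it covers only part of a hypothesis about physical and neurological function.

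**Conclusion.** The concern holds as a failure to specify. Nine primaries, an unadjusted threshold and post-hoc analysis leave no result identified in advance as showing that FES works, while the document says efficacy will be tested. The false-positive risk of that claim is uncontrolled, and the plan itself gives it no single value.

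The percentages are conditional illustrations of how far the choice of rule matters, from 0.5% under the strict reading to 20.4% under the loose one, both at correlation 0. They rest on two-sided tests, one test per instrument and equal correlation, none of which the documents state. The defect itself depends on none of these assumptions. It should be corrected before outcomes are reviewed by group.

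**What to change.** Amend XI.c.1 and XI.c.3 before any outcome is reviewed by group:

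1. Define one summary score for each of the nine instruments. Holm cannot be run without this.
2. Name one primary, preferably evaluator-blinded in Table 1 (pain NRS is not) and not self-reported (CUE is), and limit the success claim to the domain it measures. To keep physical and neurological function as one claim, name one instrument for each and require both at two-sided 0.05.
3. Fix one contrast: the within-subject FES minus non-FES difference at months 4 and 9, with a period term, adjusted for months 0 and 5 where measured. State the no-carryover assumption. Report the month-4 comparison between groups as a sensitivity analysis, since carryover cannot affect it.
4. State the success rule: efficacy is claimed only if the primary contrast (or both, for a pair) favours FES at two-sided 0.05.
5. Test the remaining instruments with Holm only if the primary succeeds, or report them as estimates with confidence intervals.

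If no primary is named, apply Holm across all nine. Alternatively, label all nine exploratory and remove the P<0.05 rule and the efficacy wording.

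**Cost.** Wording only; visits, data and sample size are unchanged. A sole primary at 0.05 loses no power to multiplicity but narrows the claim. A required pair needs no split of alpha, but if each has 80% power and they are independent, joint power is 0.8 × 0.8 = 64%. Holm across nine is the expensive route, given the loss of power shown above. The month-4 comparison is weak, so non-significance there is not evidence of no effect. Carryover can bias the within-subject contrast in either direction.

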make a decision to participate in the study. In addition, the candidate will be allowed to discuss the study's appointment logistics with their own care providers. Any questions the potential subject has about the study will be answered. Once the potential subject agrees to participate, the subject will be enrolled and an initial visit will be set up. The subject consent will be obtained during this initial visit before the post-consent screening is performed.

In the 3 years since opening the International Center for Spinal Cord Injury (ICSCI) in 2005 (05'-08'), we have evaluated and treated over 600 new patients with longstanding SCI (White 63.57%, Black 31.69%, American Indian 0.91%, Hispanic 0.36%, Asian 0.18%, Other 3.28%). Currently we evaluate and treat over 250 new patients annually. Of the new patients with long-standing SCI, 50% are ASIA A and B and of this subgroup, over 10% have a neurological level between C1 and C6. Using projections through 08' and bases of 850 system clients, approximately 85 patients will meet the entry criteria of ASIA A-B, neurological level C1-6 proposed in our study. Furthermore, study entry does not have to be limited to clients already within our ICSCI system. Therefore, based on this availability, we do not anticipate the recruitment of patients to be a substantive barrier to recruitment for this study.

b. Target Population:

We plan to enroll up to 30 subjects with an expected accrued number of subjects of 24 (screening failure of 6). The 24 accrued subjects will be randomized in 2 groups of 12. We are anticipating an attrition rate of 4 subjects maximum.

We plan to enroll both male and female subjects, all ethnic groups.

No specific racial or ethnic groups will be targeted by our recruitment process.

Non-English speaking subjects will not be targeted by our recruitment process.

No vulnerable population is specifically targeted by our recruitment process.

Pregnant women will be excluded from this study.

c. Recruitment Material:

Subject Recruitment Flyer: form given to ICSCI patients that fit the study criteria during a clinic visit, and posted on the ICSCI website (www.spinalcordrecovery.org).

Inclusion/Exclusion Index Card: Laminated index cards with inclusion/exclusion criteria that physician can carry.

Inclusion/Exclusion Wall Listing: Laminated listing with inclusion/exclusion criteria posted in ICSCI clinic rooms that physician can refer to.

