The study subjects will engage in an A (upper extremities FES assisted ergometry)-B (upper extremities non-FES assisted exercises) type protocol intervention in which they undergo either 4 months of FES assisted upper extremity ergometry followed by 1 month wash out period, then by 4 months of a specific, individualized, non-FES assisted exercise regimen (strengthening, stretching, splinting) or 4 months of an upper extremities non-FES assisted exercise protocol followed by 1 month wash out period, then by 4 months of FES assisted upper extremity ergometry. 12 subjects randomly selected will start with the FES assisted intervention and the other 12 subjects will start with the non FES assisted regimen. FES will be delivered using the RT300-SLSA Cycle Ergometer, Restorative Therapies, Inc. The subjects will be assessed using a battery of physical and neurological indicators before starting the intervention (time 0), after completing first 4 months of intervention (4 months), after the 1 month wash out (5 months), after completing the second 4 month of intervention (9 months) and 3 months after completing the last intervention (12 months). The evaluator will be blinded to group assignment, but we cannot use true blinding due to the intervention's sensory component. The Study Time Line is found in Figure 1.

[figure not shown]

Figure 1: Study Time Line

(1) Assessment:

The tests listed below will be performed for all subjects. The data collection schedule in Table 1.

a) Neurological Exam: This is a routine exam performed to rule out any associated lower motor neuron/peripheral nerve injury in the C1-C6 levels. Subjects will undergo testing of the deep tendon reflexes at the biceps, brachio-radialis and triceps level. This involves tapping of each specified muscle tendon with a neurologic reflex hammer.

b) Fast Urine Pregnancy Test: This is a routine exam performed for women of child bearing age who do not take any birth control prophylaxis.

c) Severity of gleno-humeral subluxation: This is a routine exam performed to assess shoulder subluxation. The space between the glenoid and head of the humerus can be visualized on plain X-rays and measured, in centimeters, to grade severity. This test is done bilaterally.

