q) Non-FES Upper Extremity Exercise: While undergoing the non-FES exercise intervention, the subjects will receive a specific, individualized exercise regimen, consisting of strengthening, stretching, splinting and any other therapeutic interventions that do not use electrical stimulation.. The subjects will remain seated in their primary wheelchair throughout the treatment. The subjects will exercise for 60 minutes/session, three times a week for 4 months.

2. Study duration and number of study visits required of research participants.

The study will last 12 months. The Study Time Line is found in Figure 1, and the Data Collection Schedule in Table 1.

(1) Assessment:

The following post-consent screening will be performed at the Initial visit:

- a. Neurological Exam (about 30 minutes)
- b. Fast Urine Pregnancy Test (about 15 minutes)

The following assessments will be performed at the Initial Visit:

- o. FES Evaluation (about 15 minutes)

The following assessments will be performed at the Initial, 4th month, 9th month, and 12th month Visits:

- c. Severity of gleno-humeral subluxation (about 30 minutes)

The following assessments will be performed at the Initial, 4th month, 5th month, 9th month, and 12th month Visits:

- d. Spasticity measurement (about 15 minutes)
- e. Capabilities of the Upper Extremity test (about 10 minutes)
- f. Jebsen-Taylor Hand Function test (about 15 minutes)
- g. Box and Blocks test (about 15 minutes)
- h. Action Research Arm test (about 20 minutes)
- i. Functional Reach test (about 5 minutes)
- j. Range Of Motion of the upper extremity joints (about 30 minutes)
- k. Numerical Rating Scale (NRS) for pain (about 1 minutes)
- l. Pulmonary Function Test (PFTs) (about 5 minutes)
- m. American Spinal Injury Association (ASIA) exam (about 60 minutes)
- n. Pain and Spasticity Medication inventory (about 10 minutes)

	Initial	4 th Month	5 th Month	9 th Month	12 th Month	Test Evaluator*	Blinded
	5 hours	4 1/2 hours	3 2/3 hours	4 1/4 hours	4 1/4 hours		
Neurological Exam	√					PI, CoI1	No
Fast Urine Pregnancy	√					N1, N2, N3	No
Shoulder X-Ray	√	√		√	√	PI, CoI3	Yes
Modified Ashworth	√	√	√	√	√	PI, CoI1	Yes
CUE	√	√	√	√	√	T1,T6	Yes
JTHF	√	√	√	√	√	T1,T6	Yes
BB	√	√	√	√	√	T1,T6	Yes
ARA	√	√	√	√	√	T1,T6	Yes
FR	√	√	√	√	√	T1,T6	Yes
ROM	√	√	√	√	√	T1,T6	Yes
Pain NRS	√	√	√	√	√	PI, CoI1, SC2	No
PFTs	√	√	√	√	√	N1, N2, N3	No
ASIA	√	√	√	√	√	PI, CoI1	Yes
Meds Inventory	√	√	√	√	√	PI, CoI1, N1, N2, N3, SC2	No
FES Eval	√					T1,T6	No

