* PI: Principal Investigator, CoI1: Co-Investigator 1, CoI3: Co-Investigator 3, T1-7: Therapist 1-7, N1: Nurse 1, N2: Nurse 2, N3: Nurse 3, SC2: Study Coordinator2.

Table 1: Data Collection Schedule

(2) Intervention:

There are a total of 96 visits: 48 FES assisted intervention visits scheduled 1 hour, 3 times a week for 4 months, and 48 non-FES assisted exercise regimen visits scheduled 1 hour, 3 times a week for 4 months.

3. Blinding, including justification for blinding or not blinding the trial, if applicable.

The evaluator will be blinded to group assignment for the following assessment, but we cannot use true blinding due to the intervention's sensory component:

- c. Severity of gleno-humeral subluxation
- d. Spasticity measurement
- e. Capabilities of the Upper Extremity test
- f. Jebsen-Taylor Hand Function test
- g. Box and Blocks test
- h. Action Research Arm test
- i. Functional Reach test
- j. Range Of Motion of the upper extremity joints
- m. American Spinal Injury Association (ASIA) exam

4. Justification of why participants will not receive routine care or will have current therapy stopped.

All subjects will continue to consistently perform their usual (“baseline”) amount of physical activity throughout the study, including performance of lower extremities assisted FES ergometry, home exercise stretching program, cardiovascular conditioning, etc. “Baseline” activity is defined as amount of physical activity performed for at least 1 month prior to enrollment. Routine care will not be interrupted.

5. Justification for inclusion of a placebo or non-treatment group.

Both groups will receive some type of intervention: upper extremity passive ergometry or FES assisted upper extremity ergometry. This way, the effect of FES application will be extracted.

6. Definition of treatment failure or participant removal criteria.

Treatment failure constitutes of:

- Increased pain (more than 3 points increase on the NRS).
- Increased shoulder subluxation (more than 1 cm).
- Decreased range of motion (more than 15 deg).

Subjects will be removed from the study if they:

- Requires significant hospitalization (that would interfere with physiologic processes proposed to be studied through the protocol, i.e. e-stim) – at the discretion of PI.
- Become pregnant.

7. Description of what happens to participants receiving therapy when study ends or if a participant's participation in the study ends prematurely.

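### The three numeric early stopping rules (pain, subluxation, range of motion) have no scheduled reading inside either 4-month treatment block, so on schedule they can act only between blocks

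*Combined protocol and SAP*

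**What the plan says.** All references are to the combined protocol and SAP.

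- **The rules.** XI.c.4, on early stopping, has a list under the subject's medical status. Besides hospitalization it contains three numeric criteria: "Increased pain (more than 3 points increase on the NRS"), a subluxation increase of more than 1 cm, and a range-of-motion loss of more than 15 degrees. They apply to individual subjects, not to the trial as a whole. No reference value is given. XI.a.6 lists the same three thresholds as treatment failure, but its removal list names only hospitalization and pregnancy.
- **The readings.** XI.a.2 introduces the list that contains the pain score and range of motion with "The following assessments will be performed at the Initial, 4th month, 5th month, 9th month, and 12th month Visits". X-rays are taken at the initial, month-4, month-9 and month-12 visits. XI.c.1 confirms the gap: "Severity of gleno-humeral subluxation, measured by X-ray (not measured at 5 months"). The pain score is short: "Numerical Rating Scale (NRS) for pain (about 1 minutes").
- **The treatment.** XI.a.1 places the first two post-baseline assessments "after completing first 4 months of intervention (4 months), after the 1 month wash out (5 months"). The second block follows, with assessments at its end (month 9) and three months later (month 12). XI.a.2 gives 48 sessions per block and 96 in total.
- **In-session safeguards.** XIII.a has the principal investigator supervise all sessions and keeps stimulation within what the participant tolerates. XI.b.2 mentions device features such as spasm detection.

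**The concern.** A rule that stops treatment on a measured change needs a measurement while treatment is being given. The schedule has none for these three variables. A subject whose pain rises by more than 3 points in the second week of FES would, on schedule, complete all 48 sessions before anyone is required to take the reading that triggers the rule.

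What is at stake is subject protection and consistent application of the rule. XI.b.3 says the device will be run in a research mode that stimulates a larger muscle set, "which is more than the standard set of muscles", and XIII.a names pain at the stimulation site as the risk of FES. Pain is also the easiest of the three variables to measure at a session. With no stated time, rater or reference value, whether a subject past the threshold is stopped depends on informal checks.

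**Working it through.** **1. The plan's own session count.** XI.a.2 gives three sessions a week for 4 months. With 4-week months, 3 × 4 × 4 = 48 per block and 2 × 48 = 96, which matches the plan.

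**2. Readings set against the blocks.** Block 1 is months 0 to 4, the washout is months 4 to 5, and block 2 is months 5 to 9 (XI.a.1). Readings are from XI.a.2 and Table 1.

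| Variable | Inside block 1 | Inside block 2 | Between blocks | After all treatment |
|---|---|---|---|---|
| Pain NRS | none | none | months 4, 5 | months 9, 12 |
| Range of motion | none | none | months 4, 5 | months 9, 12 |
| X-ray subluxation | none | none | month 4 | months 9, 12 |

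Post-baseline readings that precede any remaining treatment are therefore 2 of 4 for pain and range of motion, and 1 of 3 for X-ray.

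**3. What each reading can still do.**
- Group 1 (FES first): the first reading that can reflect FES is month 4, after 48 of 48 FES sessions. It can withhold the exercise block but cannot interrupt FES.
- Group 2 (exercise first): the readings at months 4 and 5 can withhold FES because of worsening during exercise. The first reading that can reflect FES is month 9, after 48 of 48 FES sessions, when no intervention remains. It could at most affect follow-up to month 12.

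**4. Cost of an in-session pain score.** At the plan's figure of about 1 minute, 1 × 96 sessions × 24 subjects = 2,304 minutes = 38.4 staff hours. If all 24 subjects were in a block together, the load would be 24 × 3 = 72 readings, or 1.2 hours, a week.

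**5. Why a raised score needs confirmation.** This step concerns the remedy and does not measure harm from the gap. The documents give no rate of transient pain rises, so assume that a rise above 3 points occurs at p = 0.5% to 1% of sessions.
- If one raised score ended treatment, the chance of at least one over 96 independent sessions is 1 − (1 − p)^96 = 38.2% to 61.9%, or 9.2 to 14.9 of 24 subjects.
- If two consecutive raised scores are needed, let r be the chance that a raised score is followed by another. Model the scores as a two-state Markov chain with marginal rate p, let c be the chance of such a pair within 48 sessions, and combine the two blocks as 1 − (1 − c)². The results are:

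| Repeat probability r | Stopped over both blocks | Of 24 subjects |
|---|---|---|
| r = p (independent) | 0.2% to 0.9% | 0.06 to 0.22 |
| r = 10% | 4.2% to 8.1% | 1.0 to 2.0 |
| r = 30% | 9.5% to 18.2% | 2.3 to 4.4 |

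For scale, IX.b says: "We are anticipating an attrition rate of 4 subjects maximum". Confirmation greatly reduces unwanted stops under every assumption shown. The range is still too wide to serve as an estimate.

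**The case against.** The strongest reply is that the rules are not tied to the assessment calendar. They stand beside hospitalization, pregnancy and non-compliance, which are acted on whenever they occur, and Table 1 is a data collection schedule. The principal investigator supervises every session, is a listed pain rater, and could take a 1-minute score at any time. Stimulation is limited by tolerance, and subjects may withdraw whenever they wish.

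This stands in part. Unscheduled readings are not forbidden, and in-block action is possible. But none of these safeguards states a reading of any of the three variables. Tolerance limits the current during a session. It does not show pain building up over weeks, a widening joint space or lost range.

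Two further replies have weight. XI.a.6 already treats the same thresholds as treatment failure, a use that the end-of-block readings do serve, so for X-ray and range of motion the remedy is largely wording. Also, the case report forms and Figure 1 are not in the supplied text, so a session log may exist. If one does, a cross-reference to it would largely answer the point for pain.

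A reader might go further and infer that nobody watches for pain during a block, that the rules can never act, or that subjects are harmed or the results biased. The documents do not support this. Sessions are supervised, the readings at months 4 and 5 (month 4 only for X-ray) can withhold the second block, and nothing in the text gives a rate of such worsening or a mechanism of bias.

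**Conclusion.** The point holds in this form: for each of the three numeric rules the supplied protocol schedules zero readings inside either block. On schedule, none of them can interrupt the block in which the worsening arose. They can affect treatment only at months 4 and 5 (pain and range of motion) or month 4 (X-ray). Worsening in block 2 is first read when no intervention remains.

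This rests on the written schedule and on the supplied text being complete on session procedures. It does not cover the hospitalization, pregnancy or compliance criteria, which need no scheduled reading. It should be fixed, because the gap concerns subject safety and the main part of the remedy is cheap.

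**What to change.** **Pain: add an in-block reading.**
- Record the pain NRS at each existing intervention session in both blocks.
- Have it taken by someone who is not a blinded rater. In Table 1, Study Coordinator 2 and Nurses 1 to 3 appear only in rows marked not blinded. The principal investigator, Co-Investigator 1 and Therapists 1 and 6 have blinded ratings. The text does not show who attends sessions. If the coordinator and nurses do not, use treating staff without a blinded rating task; the legend lists "T1-7: Therapist 1-7".
- Use month 0 as the reference in both blocks. A reference reset at month 5 would let a subject rise 3 points in each block, 6 above baseline, without triggering the rule. A rise from block start may be added as a second trigger.
- On a rise above 3 points, hold or reduce stimulation and recheck at the next session before resuming. If the rise is confirmed, end that block's intervention but keep the remaining assessment visits.

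**X-ray: describe it as an end-of-block criterion against month 0.** This is wording only and adds no radiation. Resetting the reference at month 4 would allow 1 cm in each block, 2 cm in total, to pass.

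**Range of motion: treat it the same way**, unless existing treating staff without a blinded rating task can make brief in-block checks.

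**Cost.** About 38 staff hours over the trial for the pain score, with no extra visits. The downside is possibly a few additional early stops, at a rate the documents do not allow to be estimated. The confirmation step limits their number, and keeping the assessment visits limits the loss of data. The thresholds themselves remain the investigators' choice.
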